6.3 Discontinuation

6.3.1 *Treatment Discontinuation*

If at any time during the study the investigator determines that it is not in the best interest of the subject to continue treatment, the subject's treatment will be discontinued. The investigator can discontinue the treatment for a subject at any time if medically necessary. If a subject's treatment is permanently discontinued by the investigator because of an AE, that AE should be indicated as the reason for treatment discontinuation. In this case, the subject is discontinued from the treatment, but still participates in the study and the subject is encouraged to follow the visit schedule and complete all assessments.

In addition, the investigator may instruct the subject to temporarily halt treatment of a specified region (i.e., due to an adverse event). This treatment modification and the reason for the temporary drug interruption should be documented in the subject's source documents and eCRF. The lesions in the impacted area should continue to be counted in the lesion count during the period of treatment modification.

The investigator may discontinue a subject's treatment if the subject/caregiver has failed to follow study procedures or to keep follow-up appointments. Appropriate documentation in the subject's study record and the study database regarding the reason for treatment discontinuation must be completed.

Reasons for an investigator's withdrawal of a subject **from the treatment** may include, but are not limited to, the following:

- Safety (e.g., severe adverse reactions, pregnancy)

- When a concomitant medication or treatment likely to interfere with the results of the study is reported, or required, by the subject, the investigator will decide, in consultation with the CRO whether the subject is to be withdrawn.

Reason(s) for discontinuation from the treatment as listed in the study record will be entered into the study database as follows:

- Completed (complete clearance prior to Week 12)
- Adverse Event (including LSRs deemed to be significant by investigator)
- Withdrawal by Subject/Caregiver
- Physician Decision
- Protocol Violation
- Lost to Follow-Up
- Pregnancy
- Lack of Efficacy
- Worsening of Molluscum Contagiosum
- Other

6.3.2 *Study Discontinuation*

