A subject/caregiver may voluntarily withdraw from study participation at any time. If the subject/caregiver withdraws consent and discontinues from the study, the investigator will attempt to determine the reason for discontinuation and record the reason in the subject's study records and in the study database. In the event of discontinuation from the study, (i.e., prior to Week 12/ET1) every effort should be made to have the subject return to the study center to complete the Week 12 evaluations (ET1 visit). Subjects who withdraw from the study will not be replaced. Subjects who discontinue from the study after Week 12 but prior to Week 24 will be asked to return to the study center to complete the Week 24 evaluations (ET2 visit).

All subjects who fail to return to the study center will be contacted by telephone to determine the reason(s) why the subject failed to return for the necessary visit or elected to discontinue from the study. If a subject/caregiver is unreachable by telephone after a minimum of two documented attempts (one attempt on two different days), a certified letter will be sent requesting that the

subject contacts the investigator. These actions will be reported on the subject's study record and a copy of the follow-up letter maintained in the investigator's file.

An investigator may withdraw a subject from the study when a subject is lost to follow-up.

All premature discontinuations and their causes must be carefully documented in the subject's study record and in the study database.

All Week 12 or Week 24 evaluations should be performed at the time of premature discontinuation as applicable. All data gathered on the subject prior to termination will be made available to the CRO. The investigative site should make all reasonable efforts to ensure the subject returns to complete the appropriate termination visit, even if the subject is not able to attend other study visits.

Study completion or reason(s) for discontinuation from the study as listed in the study record will be entered into the study database as follows:

- Completed Treatment Per Investigator's Instructions and Completed All Study Visits
- Withdrawal by Subject/Caregiver
- Lost to Follow-Up

Novan has the right to terminate or stop the study at any time. Should this be necessary, the investigator will ensure that proper study discontinuation procedures are completed.

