7.3 Protocol Deviations

This study will be conducted as described in this protocol, except for in emergency situations in which the protection, safety, and well-being of the subject requires immediate intervention, based on the judgment of the investigator (or a responsible, appropriately trained professional designated by the investigator). In the event of a significant deviation from the protocol due to an emergency, accident, or mistake, the investigator or designee must contact the CRO at the earliest possible time by telephone. This will allow an early joint decision regarding the subject's continuation in the study. This decision will be documented by the investigator and the CRO.

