12 STATISTICAL METHODS

12.1.1 *Demographic and Baseline Characteristics*

Subject demographic and Baseline characteristics will be summarized by treatment group for the SAF, ITT, and PP populations. Relevant medical history, current medical conditions, and any other relevant information will be listed by subject.

12.1.2 *Efficacy Analysis*

The primary efficacy endpoint, proportion of subjects with complete clearance of all treatable molluscum lesions at Week 12 in the ITT, will be analyzed using a generalized estimating equation (GEE) for logistic regression with an exchangeable working correlation structure. The model will include treatment, investigator type (dermatologist vs other), household number of randomized subjects (1 subject per household vs 2 subjects per household), age and Baseline lesion count as factors. The odds ratio between SB206 12% and vehicle gel, 95% CIs for the odds ratio, and *P*-value for the covariate-adjusted treatment comparison will be presented. Only subjects who achieve complete clearance at Week 12 will be counted as responders for the primary analysis; all other subjects (e.g., those who discontinue the study before achieving complete clearance) will be reported as failures. As a sensitivity analysis, the primary efficacy analysis will also be reported for the PP population.

The familywise error rate with respect to the primary endpoint and secondary endpoint will be strongly controlled at the alpha=0.05 level using a fixed-sequence method testing strategy. If the primary endpoint is not statistically significant at the alpha=0.05 level, the secondary efficacy endpoint will be considered not significant. If the primary endpoint is statistically significant at the alpha=0.05 level, the secondary efficacy endpoint will be analyzed.

- Proportion of all study subjects demonstrating complete clearance of all treatable MC at Week 8

If the secondary efficacy endpoint fails to reach statistical significance at the alpha=0.05 level, it will be considered not statistically significant.

The dichotomous secondary efficacy endpoint will be analyzed using the GEE model described for the primary efficacy endpoint. Other sensitivity analyses may be performed and will be specified in the SAP.

The analyses methods to be used for the exploratory endpoints will be detailed in the SAP, including any additional exploratory analyses that may be conducted. The SAP will be finalized before unblinding and database lock.

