9.5 Protocol Deviations

Significant protocol deviations that could potentially affect the efficacy or safety conclusions of the study will be identified prior to database lock and unblinding of individual subject treatment information. Significant protocol deviations may include, but are not limited to:

- Randomly assigned subjects who did not satisfy selected inclusion and exclusion criteria
- Randomly assigned subjects who developed withdrawal criteria during the study but were not withdrawn
- Subjects who were randomized incorrectly including subjects of the same household who are randomized to different treatments
- Subjects who received the wrong treatment
- Subjects where the subject/site staff were unproperly unblinded
- Week 12 Lesion Count not performed
- Subjects who received an excluded concomitant treatment.

The decision on the criteria for whether a subject is excluded from the PP Population will be made during the data review meeting prior to unblinding and database lock. Reasons for exclusion of a subject from the analysis will be listed.

A listing of all protocol deviations including the deviation designation (major or minor and significant or not), category, and indication of whether the deviation led to an exclusion of a subject from the PP Population will be presented in a data listing.

Major and significant protocol deviations will be summarized by deviation category and treatment group.

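### Protocol 7.3 and 8.4 allow a subject to be taken out of the study after a deviation or unblinding, which does not fit 6.3 and can turn an observable Week 12 outcome into an imputed failure

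*Combined protocol and SAP*

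**What the plan says.** **Protocol 7.3.** The trigger reads "In the event of a significant deviation from the protocol due to an emergency, accident, or mistake". The site must then telephone the CRO, with this purpose: "This will allow an early joint decision regarding the subject's continuation in the study". The decision is documented. No criterion for staying or leaving is given.

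**Protocol 8.4.** After an individual unblinding, the investigator, having consulted the medical monitor, decides whether the subject is asked to withdraw from the study.

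**Protocol 6.3.1.** Stopping drug is kept apart from leaving the study. For a permanent stop because of an adverse event, "the subject is discontinued from the treatment, but still participates in the study". Protocol Violation appears in the list introduced by "Reason(s) for discontinuation from the treatment as listed in the study record will be entered into the study database as follows". Consultation with the CRO over an interfering medication also falls under withdrawal from treatment.

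**Protocol 6.3.2.** The database categories for the end of study participation are completion, withdrawal by subject or caregiver, and lost to follow-up. The one investigator ground stated there is: "An investigator may withdraw a subject from the study when a subject is lost to follow-up". Withdrawn subjects are not replaced. An ET1 visit with the Week 12 evaluations is requested from anyone who leaves before Week 12.

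**Analysis rules.** Under protocol 12.1.2 only clearance at Week 12 is a response, and "all other subjects (e.g., those who discontinue the study before achieving complete clearance) will be reported as failures". SAP 10.4 treats a missing response as non-response. SAP 7 (final version) maps an early-termination count by study day; the Week 12 window is Day 72 to 98.

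**SAP 9.5.** One possible significant deviation is: "Randomly assigned subjects who developed withdrawal criteria during the study but were not withdrawn". It does not say whether this means withdrawal from treatment or from the study.

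**The concern.** The primary analysis is by ITT, and the plan already has a place for deviations: the per-protocol set, settled before unblinding. Follow-up after a deviation should therefore continue. Elsewhere the protocol does this. Subjects stay under observation after an adverse-event stop (6.3.1), suspected allergic contact dermatitis (7.2.4, 7.2.5) and pregnancy (9.5), and 4.1 encourages everyone to remain for 24 weeks.

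Sections 7.3 and 8.4 depart from that. Someone removed under either has no matching exit category in 6.3.2 and may have no usable Week 12 count. The primary analysis then records a failure where an outcome could have been seen. The per-protocol analysis may lose the subject too, because a Week 12 count not performed is itself a possible significant deviation in SAP 9.5. Removal with no count on Day 44 to 71 affects the Week 8 secondary endpoint in the same way.

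Because the decision is made case by case, removal rates need not be equal between arms.

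**Working it through.** **1. How a removal becomes a failure**

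| Removal and ET1 | Week 12 result in the primary analysis |
|---|---|
| ET1 count on Day 72 to 98 | The observed count is used |
| ET1 count before Day 72 | Mapped to an earlier visit; Week 12 missing, so non-responder |
| No ET1 and no other count on Day 72 to 98 | Week 12 missing, so non-responder |

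The problem is confined to the last two rows.

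**2. The plan's own power figures**

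Inputs from protocol 11.2: 113 vehicle, 227 SB206, two-sided alpha 0.05. Pooled two-proportion z-test, independent subjects:

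power = Φ[(d − 1.96·SE0)/SE1], where
- SE0 = √[p̄(1 − p̄)(1/113 + 1/227)]
- SE1 = √[pV(1 − pV)/113 + pA(1 − pA)/227]

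For 18% against 36%:
- p̄ = (113 × 0.18 + 227 × 0.36)/340 = 0.3002
- SE0 = 0.0528 and SE1 = 0.0482
- (0.18 − 1.96 × 0.0528)/0.0482 ≈ 1.59, giving 94.4%

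The other two scenarios give 93.4% (20% against 38%) and 82.8% (20% against 35%). The plan states 94%, 93% and 83%, so its figures are reproduced and are not in dispute.

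**3. Effect of removal**

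Let w be the share of an arm removed without a usable Week 12 count. If removal is unrelated to outcome, the analysed rate is p(1 − w). The documents give no value for w, so every w below is an assumption. Planning rates are 18% and 36%.

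| w vehicle | w SB206 | Vehicle rate | SB206 rate | Difference (points) | Power |
|---|---|---|---|---|---|
| 0 | 0 | 18.0% | 36.0% | 18.0 | 94.4% |
| 1% | 1% | 17.8% | 35.6% | 17.8 | 94.1% |
| 2% | 2% | 17.6% | 35.3% | 17.6 | 93.8% |
| 5% | 5% | 17.1% | 34.2% | 17.1 | 92.8% |
| 10% | 10% | 16.2% | 32.4% | 16.2 | 90.8% |
| 0 | 2% | 18.0% | 35.3% | 17.3 | 92.7% |
| 0 | 5% | 18.0% | 34.2% | 16.2 | 89.4% |
| 0 | 10% | 18.0% | 32.4% | 14.4 | 81.7% |
| 5% | 0 | 17.1% | 36.0% | 18.9 | 96.4% |

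In subjects, 2% of 340 is about 7, and 5% of the SB206 arm is about 11 (0.05 × 227 = 11.35).

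At the plan's least favourable scenario (20% against 35%, 82.8%), 5% removal in both arms gives 80.0% and 5% from SB206 only gives 73.2%.

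Equal removal scales the difference by (1 − w), so it only dilutes. Unequal removal shifts the difference down or up according to which arm loses more.

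**The case against.** The strongest reply is that this is a loose word in 7.3 and not a defect in the design. Much of that reply stands.

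- **A reader might infer that 6.3 forbids removal for a deviation.** It does not. The sentence about still participating concerns adverse-event stops, and the loss-to-follow-up sentence is permissive. Protocol 4.1 also foresees study exit for adverse events or other reasons. The sections fail to fit together, but no express prohibition is broken.
- **The trigger is narrow.** Section 7.3 covers significant deviations from emergency, accident or mistake, requires a documented joint decision, and does not favour removal.
- **Safeguards exist.** ET1 is requested, and a count on Day 72 to 98 serves as Week 12. SAP 10.4 and 11.1 add a sensitivity analysis that counts subjects clear at their last assessment as responders, and a 14-scenario dropout analysis with 100 imputations each. These test assumptions about the missing counts. They do not recover the counts or change the primary rule.
- **A reader might infer that SAP 9.5 pushes sites to remove subjects.** The text does not support this. The item classifies deviations and reads naturally against the treatment-withdrawal reasons in 6.3.1. It needs clarifying, not deleting.
- **A reader might infer that the treatment difference must shrink, for instance because steroid use for local reactions would lead to removals on SB206.** Neither part follows. Vehicle-only removal widens the difference. On steroids the documents are inconsistent: 4.1 and 7.2.4 permit corticosteroids for local reactions, while 8.7 prohibits topical steroids on or near lesions during the study. Those passages must be reconciled, but they do not predict an excess of removals in one arm.

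**Conclusion.** The point holds as a mismatch between sections with a possible, unquantified effect on the primary endpoint. Sections 7.3 and 8.4 open a route out of the study that 6.3.2 has no category for, and anyone who takes it without a count on Day 72 to 98 is imputed as a failure.

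The likely size is small. Equal removal of 1 to 2% costs less than one point of power, and 5% costs 1.6 points (94.4% to 92.8%). The greater worry is discretionary and possibly unequal removal: 5% from one arm alone moves the 18-point difference to 16.2 (power 89.4%) or 18.9 (power 96.4%). Blinding makes such imbalance less likely but does not exclude it, least of all under 8.4, where the assignment is known.

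These figures assume removal unrelated to outcome, no usable Week 12 count in any removed subject, independent subjects and a pooled z-test in place of the planned GEE model. No removal share comes from the documents, and nothing in them shows that the primary result would change. The case for acting rests on how little the change costs.

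**What to change.** 1. **Protocol 7.3 and 8.4:** reconcile both with 6.3, so that the joint decision concerns study treatment under 6.3.1. This sets no new rule on when treatment stops.
2. **Add to 7.3 and 8.4:** *A protocol deviation or an unblinding is not in itself a reason to end follow-up. Unless consent is withdrawn, scheduled visits continue and the Week 8 and Week 12 lesion counts are performed. The deviation is handled through the per-protocol population.*
3. **SAP 9.5:** keep the withdrawal-criteria item, and specify that it means withdrawal from treatment under protocol 6.3.1.

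The cost is a few sentences in the protocol and a clarification in the SAP. There are no visits beyond those already scheduled, the right to withdraw is untouched, and the stated power of 94%, 93% and 83% needs no revision.

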8 STUDY DRUG MANAGEMENT

8.1 Description

8.1.1 *Formulation*

Investigational Drug: SB206 12%	Comparator Drug: Vehicle Gel
Dosing: Up to approximately 2mL of SB206 QD	Dosing: Up to approximately 2mL of Vehicle Gel QD

8.1.2 *Storage*

Upon receipt from Novan, or Novan's designee, a study staff member will place all study supplies in a refrigerated temperature-controlled and monitored area. The SB206/Vehicle study product should be refrigerated (2-8°C/36-46°F) until dispensed.

Access to study supplies should be strictly limited to the study staff. Neither the investigator nor any member of the study staff will distribute any of the study supplies to any person not participating in this study.

If a study staff member becomes aware that the study supplies have not been properly handled (i.e., supply arrives and was not placed in refrigerator upon receipt or there is a temperature excursion during shipment), the CRO must be contacted immediately. In such an event, study supplies should be quarantined and not be administered to any subject until Novan or Novan's designee provides further direction.

It is expected that the site staff will maintain refrigerator temperature logs in the refrigerated study drug storage area, recording the temperature at least once each working day. Excursions in temperature during storage should be discussed with the CRO immediately and study supplies should be quarantined and not administered until Novan provides approval for use. Other supplies will be stored at room temperature.

The study drug will be dispensed at the discretion of and by the direction of the designated study personnel in accordance with the conditions specified in this protocol. It is the investigator's responsibility to ensure that accurate records of study drug dispensing and return are maintained.

8.2 Packaging and Shipment

Novan, or designee, will provide all study drug to the sites. Sites are required to maintain all records of shipment and receipt in the Investigator Site File.

8.3 Method of Assigning Subjects to Treatment Groups

In this randomized, double-blind, vehicle-controlled study, subjects who meet study entry criteria will be randomly assigned in a 2:1 ratio (active: vehicle). The randomization schedule will be computer generated using a permuted block algorithm and will randomly allocate IP to randomization numbers. The randomization numbers will be assigned sequentially through a central IWRS as subjects are entered into the study. At randomization, subjects will be stratified into four strata corresponding to the cross-classification of household number of randomized subjects (1 subject per household vs 2 subjects per household) and investigator type (dermatologist vs other). Households randomizing 2 subjects would receive the same treatment assignment for both subjects. Approximately 340 subjects, 6 months of years of age and older, with a minimum of 3 and a maximum of 70 lesions at Baseline will be randomized.

8.4 Blinding and Unblinding Treatment Assignment

All subjects, investigators, and study personnel involved in the conduct of the study will be blinded to treatment assignment, with the exception of a specified unblinded statistician who will generate and have access to the randomization code. The unblinded study personnel will not otherwise participate in study procedures or data analysis prior to unblinding of the study data to all study related personnel.

When approximately 200 subjects (cumulative across studies NI-MC302 and NI-MC302) have completed 4 weeks of treatment, a DSMB will review all available unblinded safety data (including patch testing). Personnel who are not otherwise involved in the study will prepare the unblinded data and summary tables for this analysis.

Study personnel will endeavor to safeguard the integrity of the study blind to minimize bias in the conduct of the study. Individual treatment unblinding is discouraged since knowledge of the treatment assignment will not materially change the planned management of a medical emergency. Unblinding should be discussed in advance with the medical monitor if possible. Study personnel will utilize the IWRS for emergency unblinding. If the investigator is not able to discuss treatment unblinding in advance, then he or she must notify the CRO medical monitor as soon as possible about the unblinding incident without revealing the subject's treatment assignment. The investigator or designee must record the date and reason for study discontinuation on the appropriate eCRF for that subject. In all cases that are not emergencies, the investigator must discuss the event with the medical monitor prior to unblinding the subject's treatment assignment.

If treatment assignment is unblinded for an individual subject, study personnel will be notified of that subject's treatment assignment without unblinding the treatment assignments for the remaining subjects in the study. Thus, the overall study blind will not be compromised. If a subject's treatment assignment is unblinded, he or she may or may not be asked to withdraw from the study. The investigator will make this decision after consultation with the medical monitor.

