4 STUDY PLAN

4.1 Study Design

This is a Phase 3 multi-center, randomized, double-blind, vehicle-controlled, parallel group study to be conducted in approximately 340 subjects with MC. After obtaining informed consent/assent, subjects who satisfy entry criteria will be randomized 2:1 (active:vehicle). Subjects receiving current treatment for MC at the time of the Screening Visit will enter a wash out period of up to 14 days prior to randomization. In the event no wash out period is required. Screening and Baseline visit activities may be combined into a single visit. At randomization, subjects will be stratified into four strata corresponding to the cross-classification of household number of randomized subjects (1 subject per household vs 2 subjects per household) and investigator type (dermatologist vs other). Households randomizing 2 subjects will receive the same treatment assignment for both subjects. Up to two subjects from the same household may be randomized on the same day, if both individually meet all inclusion/exclusion criteria. For subjects in the same household, Screening can occur on different days; however, the Baseline visit must occur on the same day.

Subjects or their caregivers will apply SB206 12% or Vehicle Gel once daily for a minimum of 4 weeks and up to 12 weeks to all lesions identified at Baseline and new treatable lesions that arise during the course of the study. Subjects or their caregivers will continue to treat the area until the next scheduled visit even if the lesion(s) clear. If the investigator determines all lesions are cleared at a clinic visit, the treatment may stop. At Weeks 2, 4, and 8, the investigator will count and record the number of active (raised, treatable) molluscum lesions per body area. The investigator will also determine if new lesions have occurred since the last visit, and the subject or caregiver will be instructed by the investigator to re-initiate treatment. If treatment is stopped due to clearance, subjects will continue regularly scheduled visits through Week 24.

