5. DETERMINATION OF SAMPLE SIZE

Approximately 340 subjects, 6 months of age and older, with a minimum of 3 and a maximum of 70 MC lesions at Baseline will be randomized in a 2:1 (active:vehicle) scheme. The sample size assumptions for this study were informed by the completed Phase 2 study NI-MC201 of subjects 2 years of age and older with between 3 and 70 MC lesions at Baseline. In the Intent-to-Treat (ITT) Population of the Phase 2 study, the observed rates of complete clearance at Week 12 were 18% (12/66) for vehicle and 38% (18/48) for SB206 12% QD and the covariate-adjusted treatment difference was 18%.

A sample size of 340 subjects (227 subjects in the SB206 12% QD group and 113 subjects in the vehicle group) will provide 94% power for a 2-sided alpha test of size 0.05 to detect an absolute difference of 18% when the vehicle response rate is 18%. This same sample size provides 93% power to detect a treatment difference of 18% when the vehicle response rate is 20% and 83% power when the treatment difference is 15% and the vehicle response rate is 20%.

Since the intra-cluster correlation is estimated to be small (<10%) and the average size of households is expected to be capped at roughly 1.3, the sample size is still sufficient when considering the fact that the subjects within the household may not be independent.

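### Protocol 8.4 says unblinding one subject leaves all others blinded; this is untrue for two-subject households, and an investigator who knows the arm may then decide on study withdrawal

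*Combined protocol and SAP*

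**What the plan says.** Protocol 8.4 (Blinding and Unblinding) provides that, when one subject is unblinded, study personnel are told that subject's arm "without unblinding the treatment assignments for the remaining subjects in the study". It concludes: "Thus, the overall study blind will not be compromised". Of the unblinded subject it says that "he or she may or may not be asked to withdraw from the study", and it leaves that decision to the investigator after consultation with the medical monitor. No criteria are given. The same section has the site enter a date and reason for study discontinuation on the eCRF.

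Protocol 4.1 says: "Households randomizing 2 subjects will receive the same treatment assignment for both subjects". Section 8.3 repeats the rule.

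Protocol 6.3.2 says: "An investigator may withdraw a subject from the study when a subject is lost to follow-up". Its exit options are completion, withdrawal by the subject or caregiver, and loss to follow-up.

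For the primary endpoint, protocol 12.1.2 says that "all other subjects (e.g., those who discontinue the study before achieving complete clearance) will be reported as failures". SAP 10.4 scores a missing response as nonresponse. SAP 9.5 lists among possible significant deviations: "Subjects where the subject/site staff were unproperly unblinded". On household size, SAP section 5 says that "the average size of households is expected to be capped at roughly 1.3". SAP references here are to the latest of the three versions in the file, the one that cites TLF shells Version 3.0.

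**The concern.** The assurance in 8.4 conflicts with the allocation rule. Anyone at the site who knows the protocol and learns one household member's arm can read off the partner's arm. Neither document makes an exception for the partner or says how the partner's blind status is to be recorded.

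This matters because the site's own staff score the outcomes. The primary endpoint is a lesion count that requires judgement on clustered lesions and on what is still raised and palpable (7.1.1). The distinction between BOTE and local skin reaction (7.2.3, 7.2.4) and adverse event causality (9.3) are also judgements. The partner would go on being assessed by people who know the arm, with nothing in the data to show it.

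The second issue is withdrawal. Elsewhere the protocol keeps subjects in follow-up when study drug stops (6.3.1, 7.2.4, 7.2.5, 9.5). Section 8.4 instead opens a route out of the study, decided by someone who knows the arm, and leaving early enough turns a binary primary outcome into a failure.

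**Working it through.** **1. The plan's own power figure.** Inputs from protocol 11.2: 227 and 113 subjects, two-sided alpha 0.05, vehicle 18%, SB206 36%. A pooled-variance two-proportion z-test gives:

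- pooled rate = (113 × 0.18 + 227 × 0.36)/340 = 0.300
- SE under the null = √[0.300 × 0.700 × (1/113 + 1/227)] = 0.0528
- SE under the alternative = √[0.18 × 0.82/113 + 0.36 × 0.64/227] = 0.0482
- power = Φ[(0.18 − 1.96 × 0.0528)/0.0482] = 94.4%, against 94% stated

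The other two stated scenarios give 93.4% and 82.8%, against 93% and 83%. The plan's figures reproduce, and the same test is used in step 4.

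**2. How many subjects have a household partner.** With one or two subjects per household and mean size m, there are 340/m households. A fraction m − 1 of them have two subjects, so the share of subjects with a partner is 2(m − 1)/m.

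| Mean size m | Households | Two-subject households | Subjects with a partner |
|---|---|---|---|
| 1.3 (SAP cap) | 262 | 78 | 157 (46%) |
| 1.2 (assumed) | 283 | 57 | 113 (33%) |
| 1.1 (assumed) | 309 | 31 | 62 (18%) |

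For these subjects, unblinding either member discloses two arms, barring an allocation error (SAP 9.5 lists household members randomized to different arms as a deviation).

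**3. When withdrawal decides the primary outcome.** SAP section 7 maps an early termination visit by study day, with Day 72 to 98 as Week 12.

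- No lesion count in Day 72 to 98: Week 12 is missing and scored as nonresponse, even if an earlier termination count was zero. An unperformed Week 12 count is also a listed deviation in SAP 9.5, so the subject may leave the per-protocol set as well.
- Termination visit within Day 72 to 98: the count becomes the Week 12 value and can be a response.
- Withdrawal after the Week 12 visit: no effect on the primary outcome.

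**4. Possible size of the withdrawal effect.** The documents do not give the number of unblindings, so k below is assumed. Subjects are treated as independent and covariates are ignored. The k subjects would otherwise have responded at their arm's average rate, and all are in one arm.

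True rate 18% in both arms, k vehicle subjects forced to failure, so the vehicle rate becomes 0.18 × (1 − k/113):

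| k | Vehicle rate | Chance of a false finding favouring SB206 |
|---|---|---|
| 0 | 18.0% | 2.5% |
| 2 | 17.7% | 2.9% |
| 4 | 17.4% | 3.4% |
| 10 | 16.4% | 5.3% |

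True rates 36% and 18%, k SB206 subjects forced to failure, so the SB206 rate becomes 0.36 × (1 − k/227): power falls from 94.4% to 93.7%, 92.9% and 90.1% for k = 2, 4 and 10.

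**The case against.** The strongest reply is that this will rarely arise. Section 8.4 discourages individual unblinding because knowing the arm would not materially change emergency care, and the Phase 2 study of 256 subjects had no deaths or serious adverse events (1.1.4). The medical monitor must be consulted on withdrawal and, where an emergency unblinding precedes discussion, is to be notified without being told the arm. The latest SAP (11.1) already has an analysis counting clearance at the last assessment as response, and a dropout grid of 14 response-probability pairs. All of this stands and keeps the point small. None of it makes the assurance true for a partner, and the sensitivity analyses probe the primary result without changing it.

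Several stronger readings are tempting but unsupported:

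- A reader might infer that withdrawal always makes the subject a failure. Step 3 shows that it does so only when no count falls in Day 72 to 98.
- A reader might infer that SAP 9.5 treats only the index subject as a deviation. Its list is open-ended, its wording reaches site staff, and per-protocol criteria are settled at a data review meeting before unblinding. A partner could be caught if the unblinding was improper. What is missing is a rule that ensures it.
- A reader might infer that the family is unblinded too. Section 8.4 speaks of notifying study personnel and does not say that the subject or caregiver is told.
- A reader might infer that 6.3.2 forbids withdrawal after unblinding. Its sentence on loss to follow-up is permissive, and a subject who agrees to leave fits the existing code for withdrawal by subject or caregiver. What remains is an eCRF instruction worded as if discontinuation follows from unblinding, although 8.4 makes it optional.

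**Conclusion.** The point holds in a limited form. The assurance in 8.4 is incorrect by design for two-subject households, and no rule covers the partner's blind status. The same section leaves a withdrawal decision, without criteria, to an investigator who knows the arm; for a subject left without a count in Day 72 to 98, that decision produces a primary-analysis failure.

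The 46% (157 of 340) is an upper figure resting on the SAP's cap of 1.3, and it counts subjects with a partner, not subjects whose blind would be broken. The effect on the result depends on an unknown number of unblindings. With two to four subjects, all in the vehicle arm, the chance of a false finding favouring SB206 rises from 2.5% to between 2.9% and 3.4%. It reaches 5.3% only with ten. The case for change is that a false statement about the blind and an avoidable arm-aware route to failure can be removed at little cost. It is not that the trial's conclusion is at serious risk.

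**What to change.** 1. **Protocol 8.4, assurance.** Say that unblinding one member of a two-subject household also discloses the other's arm to the personnel informed, and record both members as unblinded, with the date.
2. **SAP 9.5.** Apply the unblinding flag and the blinded per-protocol review to both members.
3. **Protocol 8.4, withdrawal.** State that unblinding alone is not a reason for study withdrawal, and that scheduled lesion counts continue through Week 12 and follow-up through Week 24. Reconcile the eCRF sentence on the reason for study discontinuation with 6.3.2. Decisions about study drug stay under 6.3.1.

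Requiring a different lesion counter after unblinding is not part of this recommendation. Section 7.1.1 allows another evaluator only in unforeseen circumstances and stresses the same one at Baseline and Week 12, so a switch would trade blinding against counting consistency.

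The cost is wording in two documents and one extra data flag. The downside is a few more subjects flagged or excluded from the per-protocol population.
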